##### **4.2.7.1.6.1 Hypoglycemia**

Separate pages to capture events of hypoglycemia are contained within the CRF.

Hypoglycemic events with an onset from Day 1 of the double-blind treatment period up to and including 4 days (30 days for SAE) after the last dose date in the double-blind treatment period will be considered as occurring during the double-blind treatment period. The

proportion of patients with hypoglycemic events will be tabulated by treatment group in the double-blind treatment period. Both primary and sensitivity safety analyses will be performed. Hypoglycemic events will be categorized using the following classes:

- Major episodes of hypoglycemia - defined as symptomatic episodes requiring external (3rd party) assistance due to severe impairment in consciousness or behaviour, with a capillary or plasma glucose value  $<3$  mmol/L ( $<54$  mg/dL), and prompt recovery after glucose or glucagon administration,
- Minor episodes of hypoglycemia - defined as either a symptomatic episode with a capillary or plasma glucose measurement below 3.5 mmol/L (63 mg/dL) regardless of need for external assistance, or an asymptomatic capillary or plasma glucose measurement below 3.5 mmol/L (63 mg/dL), that does not qualify as a major episode,
- Other episodes of hypoglycemia - defined as episodes reported by the investigator that are suggestive of hypoglycemia but do not meet the above criteria.

When summarizing hypoglycemic events leading to discontinuation no upper cutoff day windows are applied.

A listing of patients will be produced and it will display all hypoglycemic events with an onset on or after the start date of double-blind treatment period.

#### **4.2.7.1.6.2 DKA**

Separate pages to capture all potential events of DKA, signs and symptoms, and risk factors are contained within the CRF.

DKA events with an onset from Day 1 of the double-blind treatment period up to and including 4 days (30 days for SAE) after the last dose date in the double-blind treatment period will be considered as occurring during the double-blind treatment period. DKA events will be adjudicated, and the proportion of patients with DKA events overall as well as by adjudicated result will be tabulated by treatment group in the double-blind treatment period.

A listing will display all adjudicated DKA events as well as the corresponding signs and symptoms and risk factors with an onset on or after the start date of double-blind treatment period.

#### **4.2.7.2 Clinical Laboratory Tests Evaluation**

Unless otherwise specified, laboratory data obtained after the start of study medication dosing up to and including 4 days (30 days for liver function laboratory test) after the last double-blind dosing date will be considered as obtained during the double-blind treatment period. Laboratory data obtained from the day after the last study medication +4 days (30 days for liver function laboratory test) up to the last visit date of the follow-up period will be considered as obtained during the follow-up period.

For liver safety, a summary of proportion of patients with elevated liver test (see Appendix C for definition) will be provided for the double-blind treatment period. In addition, a summary of proportion of patients with elevated liver test and/or reported AE of hepatic disorder will also be provided for the double-blind treatment period.

All scheduled laboratory evaluations are performed by central laboratories. All laboratory evaluations performed by central laboratories will be included in summary tables.

Laboratory parameters will be presented in international system units, except for those listed in Table 16, which will be presented in conventional units (C) and international system units (SI).

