6.3 Recording of adverse events

6.3.1 Time period for collection of adverse events

AEs will be collected from the start of the placebo lead-in period throughout the treatment period (Visit 2 to 8) and including the follow-up period (Visit 9).

SAEs will be recorded from the time of informed consent is obtained until the end of the study (Visit 9).

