### **Follow-up Period (V8 to V9, 3 weeks)**

After completion of the treatment period, patients will enter a 3-week safety follow-up period without study drug. At the follow-up visit (Visit 9 (FU)) any changes in physical signs, renal function (*i.e.*, changes in eGFR), symptoms or laboratory parameters that may be related to dapagliflozin will be evaluated. Patients who discontinue study drug will remain in the study for follow-up and complete all scheduled study visits through Week 27. At the time of discontinuation the Week 24 procedures will be performed. Patients will not receive double-blind study drug during this follow-up period, but will complete all scheduled study visits and procedures.

The total planned study duration from Visit 1 to the safety follow-up (Visit 9) will be 33 weeks.

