#### **4.2.7 Safety Variables**

The Safety Analysis Set will be used for all safety analyses, including all data after rescue during the double-blind treatment period. Sensitivity analyses on data collected prior to rescue during the double-blind treatment period will be performed for selected Adverse Events (AEs) as described in multiple sub-sections under Section 4.2.7.1.

Safety analyses will be conducted on the double-blind treatment period and follow-up period.

AEs within 4 days or SAEs within 30 days post last double-blind study medication, which are considered in the double-blind treatment period, will not be counted as AEs or SAEs during the follow-up period.

Unless otherwise specified, the safety analyses of changes from baseline to a specific time point in safety variables (e.g., laboratory parameters and vital signs) will only include patients from the Safety Analysis Set who have data available for both the baseline and the time point under consideration.

Safety data that collected before randomization will not contribute to summaries but will be listed.

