#### **4.2.7.1.3 Serious Adverse Events**

SAEs (including hypoglycemic and DKA events) with an onset from Day 1 of double-blind treatment up to and including 30 days after the last dose date in the double-blind treatment period will be considered as occurring during the double-blind treatment period.

SAEs (including hypoglycemic and DKA events) occurring during the double-blind treatment period will be summarized by SOC, PT and treatment group. In addition, the proportion of patients with related SAEs will be presented by SOC, PT and treatment group.

A listing of all SAEs will be produced, displaying all SAEs (including pre-treatment events) that occurred during the study.

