#### **4.2.7.2.2 Changes from Baseline Values for Selected Laboratory Parameters over Time**

All analyses of laboratory data will use observed data regardless of rescue. Visit windows are provided in Section 4.3.1 in order to link each laboratory test to a scheduled visit. Change from baseline during the double-blind treatment period and the follow-up period for selected laboratory parameters will be summarized by treatment group, presenting n's, means, medians, minimum, maximum, SEs:

Hematology parameters:

- hemoglobin
- hematocrit
- red blood cell (RBC) count
- white blood cell (WBC) count
- platelet count

Serum Chemistry parameters:

- aspartate aminotransferase (AST)
- alanine aminotransferase (ALT)
- alkaline phosphatase
- total bilirubin
- blood urea nitrogen (BUN)
- electrolytes - sodium, potassium, bicarbonate, chloride, magnesium, calcium
- total protein and albumin
- creatinine, serum (Scr)
- Estimated eGFR (mL/min/1.73m^2) using MDRD equation

CCI

Urine parameters:

- Creatinine

CCI

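### The 30-day rule for liver tests outlasts the 3-week follow-up, so the planned Week 27 liver rows would be filled almost only by early discontinuers

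*SAP*

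**What the plan says.** SAP 4.2.7.2 sets the period rule for laboratory data. Results obtained "up to and including 4 days (30 days for liver function laboratory test) after the last double-blind dosing date will be considered" as belonging to the double-blind period. Results from the following day up to the last follow-up visit belong to follow-up. Liver function tests therefore have a 30-day limit and all other laboratory tests a 4-day limit.

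SAP 4.2.7.2.2 promises a table for both periods: "Change from baseline during the double-blind treatment period and the follow-up period for selected laboratory parameters will be summarized by treatment group". AST, ALT, alkaline phosphatase and total bilirubin are on its list.

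SAP 1.2 (Follow-up Period) says that after treatment "patients will enter a 3-week safety follow-up period without study drug". The study plan tables (Protocol Table 1, SAP Table 2) put Visit 8 on Day 169 and Visit 9 on Day 190, each with a ±5-day window. The safety panel, which contains the liver tests (Protocol Table 3), is drawn at both visits.

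SAP 4.3.1 assigns a measurement first to a study period and then to a day window. In Table 17 the safety laboratory column gives Week 24 as Day 128 to the last day of the double-blind period, and Follow-up Week 27 as the whole follow-up period. If several results share a window, the one closest to the target day is used. The column has no separate entry for liver tests.

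**The concern.** The liver limit of 30 days is longer than the follow-up period itself. A completer's off-drug liver sample is therefore still labelled double-blind, and the follow-up period for liver tests opens only after the last visit has taken place.

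The protocol (section 4.4) gives Visit 9 the purpose of evaluating further any changes, including in laboratory parameters, that may be related to dapagliflozin. For the four liver analytes the by-visit table could not do this in completers. Its Week 27 row would show, by arm, a subset selected after randomization by stopping treatment early. It would sit beside Week 27 rows for other analytes that do include completers, and nothing in the SAP would warn the reader of the difference.

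**Working it through.** **Inputs.** Visit 8 target Day 169 and Visit 9 target Day 190, each ±5 (study plan tables). Liver limit 30 days and other laboratory limit 4 days after last dose (SAP 4.2.7.2). The documents do not state the day of a completer's last dose relative to Visit 8. Two assumptions are used: the day of Visit 8, or the day before.

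**The plan's own figure.** 190 − 169 = 21 days = 3 weeks, which agrees with the stated follow-up. The total of 2 + 4 + 24 + 3 = 33 weeks also agrees.

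**Nominal completer.**
- Last dose Day 169: gap to Visit 9 = 190 − 169 = 21 days. Liver follow-up opens on Day 169 + 31 = Day 200.
- Last dose Day 168: gap = 22 days. Liver follow-up opens on Day 168 + 31 = Day 199.
- In both cases the last visit is on Day 190, before liver follow-up opens.

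**Across the visit windows.** Visit 8 can fall on Days 164 to 174 and Visit 9 on Days 185 to 195, giving 11 × 11 = 121 pairs.

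| Last dose | Range of gap (days) | Pairs over 30 days | Pairs at or below 30 days |
|---|---|---|---|
| Day of Visit 8 | 11 to 31 | 1 of 121 | 120 of 121 (99.2%) |
| Day before Visit 8 | 12 to 32 | 3 of 121 | 118 of 121 (97.5%) |

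The exceptions need Visit 8 at or next to its earliest day and Visit 9 at or next to its latest.

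**Where the completer's Visit 9 value goes.** Labelled double-blind, it falls in the Week 24 window of Table 17. An in-window Visit 8 is at most 5 days from Day 169, while an in-window Visit 9 is at least 185 − 169 = 16 days away. Visit 8 always wins, and the Visit 9 value appears in no by-visit row. If there is no closer sample, for example because Visit 8 was missed, the Visit 9 value is reported as Week 24 although it was taken about 3 weeks off drug.

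**Who fills the Week 27 liver row.** Patients who stop drug are asked to stay on schedule through Week 27 (Protocol 3.9.2). Their Visit 9 counts as liver follow-up if the last dose was at least 31 days earlier: on or before 190 − 31 = Day 159 for a Day 190 visit, Day 154 for a Day 185 visit, and Day 164 for a Day 195 visit. The row is therefore made up almost entirely of early discontinuers.

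**With the 4-day limit.** The smallest gap is 11 days, so 0 of 121 pairs would place a completer's Visit 9 in the double-blind period.

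**The case against.** The 30-day liver rule is explicit, the same in both arms, and inclusive. It adds off-drug results to the elevated-liver-test and marked-abnormality counts rather than losing them. SAP 4.2.7.2.1 also lists every value from both periods for any patient with a marked abnormality. Safety analysis is descriptive, with no testing between arms, and the table shows n, so a nearly empty row would be visible. All of this stands. It limits the point to the by-visit liver rows and supports keeping the 30-day rule for the abnormality counts.

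The SAP can also be read differently. The rule in 4.2.7.2 applies unless otherwise specified, and Table 17 has a single safety laboratory column without defining the period boundaries for liver tests. A programmer might use the 4-day boundary throughout. The literal reading is the stronger one, because 4.3.1 assigns the period first and only 4.2.7.2 defines it for liver tests. The ambiguity is itself a reason to write the rule down.

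A reader might infer that serious adverse events have the same defect. SAP 4.2.7 refers to "AEs within 4 days or SAEs within 30 days post last double-blind study medication, which are considered in the double-blind treatment period", while Protocol 6.3.1 ends recording at Visit 9. The documents do not support that inference. An attribution limit that runs past the end of recording misassigns nothing: each SAE recorded in a completer within the limit is counted once, as on-treatment. Capping the window at Visit 9 would change no recorded count, and it would leave the difference in observed days between completers and discontinuers as it is.

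**Conclusion.** The point holds for one output: the follow-up change-from-baseline rows for AST, ALT, alkaline phosphatase and total bilirubin. Applied literally, the SAP's period rule empties those rows of almost all completers seen within the visit windows and leaves mainly early discontinuers. This conclusion is the same whether the last dose is on the day of Visit 8 or the day before.

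Three stronger readings should be avoided.
- The 97.5% and 99.2% are shares of possible day pairs. They would be shares of completers only if visit offsets were uniform and independent and no visit fell outside its window, which the documents do not say.
- The protocol does not state that Visit 9 is meant to show whether liver changes persist or reverse. The only laboratory variable with a stated 3-week post-treatment objective is eGFR, which keeps the 4-day limit in 4.2.7.2.
- The documents give no frequency for a Visit 9 value being reported as Week 24, so that consequence is possible but unsized.

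The primary analysis, eGFR and the liver-abnormality counts are unaffected. The change is still worth making, because a stated rule gives a misleading row and is cheap to correct.

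**What to change.** In SAP 4.2.7.2 and Table 17, state that by-visit liver summaries use the same 4-day cut-off as the other laboratory tests. For these rows, define the last day of the double-blind period as last dose + 4 days and the first day of follow-up as the day after. Visit 9 then fills the Follow-up Week 27 row for completers. A Visit 9 value can no longer stand in for a missing Week 24 sample in a completer seen within the visit windows. Keep the 30-day window for the elevated-liver-test and marked-abnormality counts, and say so in the same paragraph. The SAE window needs no change.

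The cost is a few lines of SAP wording and one programming rule. No new data or visits are needed.

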**Table 16 SI and C units**

Test name	SI unit	C unit
FPG	mmol/L	mg/dL
CCI		
Total Bilirubin	umol/L	mg/dL
Serum creatinine	umol/L	mg/dL
Urine creatinine	mmol/L	mg/dL
CCI		
Phosphate	mmol/L	mg/dL

CCI

#### 4.2.7.2.1 Marked Laboratory Abnormalities

Laboratory abnormalities will be evaluated based on marked abnormality (MA) criteria. Appendix C (Laboratory Abnormality Criteria) lists the pre-defined criteria for MAs. If both the baseline and on-treatment values of a parameter are beyond the same MA limit for that parameter, then the on-treatment value will be considered a MA only if it is more extreme (farther from the limit) than was the baseline value. If the baseline value is beyond the low, and the on-treatment value is beyond the high MA limit (or vice-versa), then the on-treatment value will be considered a MA. If the baseline value is not beyond either MA limit, and the post-baseline value is beyond either MA limit, then the post-baseline value will be considered MA.

Laboratory MAs occurring during the double-blind treatment period will be summarized by treatment group for primary and sensitivity safety analysis. The directions of changes (high or low) in MAs will be indicated in the tables.

Additionally, for each patient with a MA for a parameter, all the patient's values of that parameter over the double-blind treatment period and the follow-up period will be listed.

#### **4.2.7.2.2 Changes from Baseline Values for Selected Laboratory Parameters over Time**

All analyses of laboratory data will use observed data regardless of rescue. Visit windows are provided in Section 4.3.1 in order to link each laboratory test to a scheduled visit. Change from baseline during the double-blind treatment period and the follow-up period for selected laboratory parameters will be summarized by treatment group, presenting n's, means, medians, minimum, maximum, SEs:

Hematology parameters:

- hemoglobin
- hematocrit
- red blood cell (RBC) count
- white blood cell (WBC) count
- platelet count

Serum Chemistry parameters:

- aspartate aminotransferase (AST)
- alanine aminotransferase (ALT)
- alkaline phosphatase
- total bilirubin
- blood urea nitrogen (BUN)
- electrolytes - sodium, potassium, bicarbonate, chloride, magnesium, calcium
- total protein and albumin
- creatinine, serum (Scr)
- Estimated eGFR (mL/min/1.73m^2) using MDRD equation

CCI

Urine parameters:

- Creatinine

CCI

#### **4.2.7.2.3 Additional Laboratory Data Summaries**

##### Shift Tables for Electrolytes (Sodium, Potassium, Calcium, Phosphate, and Magnesium) Categories

Shift tables of Safety Data Set patients with electrolytes values in categories of low, normal, and high (based on normal range of central laboratory) will be summarized by treatment group using the highest (for sodium, calcium, phosphate, and magnesium) and lowest (for sodium, potassium, and calcium) values (regardless of rescue) obtained during the double-blind treatment period.

CCI

will be summarized by treatment group using the Week 24 values (the last observation regardless of rescue prior to Week 24 will be used if no Week 24 measurement is available).

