3.2 Exclusion criteria

Patients should not enter the study if any of the following exclusion criteria are fulfilled:

Sex and Reproductive Status

1. Women of childbearing potential (WOCBP) who are unwilling or unable to use an acceptable method to avoid pregnancy for the entire study period.
2. Women who are pregnant or breastfeeding.
3. Women with a positive pregnancy test on enrolment or prior to study drug administration.

Central Laboratory Test Findings (from blood samples obtained at Visit 2)

4. Aspartate Aminotransferase (AST) >3X ULN.
5. Alanine Aminotransferase (ALT) >3X ULN.
6. Total Bilirubin (TB) >2 mg/dL (35 µmol/L).
7. Serum Potassium (K) >5.5 meq/L (5.5 mmol/L).
8. Serum Calcium (Ca) <8 mg/dL or > ULN (<1.99 mmol/L or > ULN).
9. Positive for hepatitis B surface antigen.
10. Positive for anti-hepatitis C virus antibody.
11. Hemoglobin ≤9.0 g/dL (90 g/L).

Target Disease Exceptions

12. History of diabetes insipidus.
13. Symptoms of poorly controlled diabetes that would preclude participation in this study including but not limited to marked polyuria and polydipsia with greater than 10% weight loss during the three months prior to signing the consent at visit 1, or other signs and symptoms.
14. History of diabetic ketoacidosis or hyperosmolar nonketotic coma.
15. History of ≥2 major hypoglycemic events in the 3 months prior to enrolment, defined as symptomatic events requiring external assistance due to severe impairment in consciousness or behaviour, with blood glucose level <3.0 mmol/L, <54 mg/dL (plasma glucose level <3.5 mmol/L, <63 mg/dL) and prompt recovery after glucose or glucagon administration.

Medical History and Concurrent Diseases

CV/Vascular diseases:

16. Severe uncontrolled hypertension defined as SBP ≥180 mmHg and/or DBP ≥110 mmHg at any visit up to randomization.

Any of the following CV/Vascular Diseases within 3 months of prior to signing the consent at visit 1:

17. Myocardial infarction.
18. Cardiac surgery or revascularization (CABG/PTCA).

19. Unstable angina.
20. Unstable heart failure (HF).
21. HF New York Heart Association (NYHA) Class IV.
22. Transient ischemic attack (TIA) or significant cerebrovascular disease.
23. Unstable or previously undiagnosed arrhythmia.

Renal Diseases:

24. Rapid worsening of renal function from Visit 1 to Visit 3 defined as >25% decrease in eGFR* from Visit 1 to Visit 3.

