#### **4.1.10 Summaries of Shifts from Baseline in Categorical Variables**

Changes from baseline in certain categorical variables will be summarized using shift tables. Frequencies and percents of patients within each treatment group will be generated for levels of cross-classifications of baseline and the on-treatment value of the variable. The on-treatment value can be either the value at a certain time point, (for example, laboratory tests) or the minimum/maximum value in the direction of toxicity, which has been observed during a study period. Treatment group differences will not be assessed in summaries of shifts.

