#### **4.2.4 Current and Concomitant Medications**

Current and concomitant medications will be summarized using the Safety analysis set by drug class (anatomic class and therapeutic class), generic drug name and treatment group, as defined by the AstraZeneca Drug Dictionary most current at time of database lock. A summary will be produced for each of the following:

- all current medication
- all concomitant medication
- all concomitant diuretic medication
- all concomitant ARB and/or ACE-I medication
- all concomitant anti-hypertensive medication

Current medications are defined as medications with a start date prior to the first day of double-blind treatment period and without a stop date prior to the consent date, i.e. current

medication will be any medication with at least 1 dose taken on or after the day of consent date up to the day prior to the first dose of study medication.

Concomitant medication during the double-blind treatment period is defined a medication with either

- a recorded medication start date falling within the double-blind treatment period, or
- a recorded medication start date prior to the first day of study medication during the double-blind treatment period without any recorded medication stop date prior to the start of the double-blind treatment period.

This means that concomitant medications for the double-blind treatment period will be any medication taken from start of the double-blind treatment period up to the end of the double-blind treatment period.

Missing and partial date handling of start and stop dates of previous, current and concomitant medications, is described in Section 4.3.6.

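### The potassium shift table uses only each patient's lowest on-treatment value, so it will understate shifts to high potassium

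*SAP*

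**What the plan says.** SAP 4.2.7.2.3 (Additional Laboratory Data Summaries) heads the display "Shift Tables for Electrolytes (Sodium, Potassium, Calcium, Phosphate, and Magnesium) Categories" and sorts patients with "electrolytes values in categories of low, normal, and high (based on normal range of central laboratory" into a table by treatment group. Two lists say which on-treatment value is used: "highest (for sodium, calcium, phosphate, and magnesium) and lowest (for sodium, potassium, and calcium) values (regardless of rescue) obtained during the double-blind treatment period". Sodium and calcium are in both lists, phosphate and magnesium only in the first, and potassium only in the second.

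The general rule is in SAP 4.1.10. A shift table may use the value at a given time point or "the minimum/maximum value in the direction of toxicity". That section does not say which direction applies to which analyte.

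Potassium appears in four other relevant places:
- **Protocol 3.2, exclusion 7:** "Serum Potassium (K) >5.5 meq/L (5.5 mmol/L"). No exclusion for low potassium is listed.
- **SAP Appendix C:** marked-abnormality limits on both sides, ≤2.5 and ≥6.0 mmol/L.
- **SAP 4.2.7.2.1:** marked abnormalities are tabulated by direction, and all values of the parameter are listed for each patient who has one.
- **SAP 4.2.7.2.2:** change from baseline in potassium is summarised with n, mean, median, minimum, maximum and SE.

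**The concern.** A table with a high column invites the reader to treat that column as the number of patients whose potassium went above normal. When patients are classified by their lowest value, the column instead counts those whose potassium never came down into the normal range on treatment. The two counts can differ many-fold, and nothing in the table's description warns of this.

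The population makes the high side relevant. The protocol title names renal safety in CKD stage 3A, high potassium at entry is an exclusion, and Appendix C sets a high limit as well as a low one. The documents thus treat potassium as a concern in both directions, but the shift table covers only one of them properly. At stake is the descriptive safety account of moderate potassium rises, those above normal but below the marked-abnormality limit. No efficacy conclusion is involved.

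**Working it through.** The documents state no figure for this table, so there is nothing to reproduce. The check is one of logic, followed by an illustration.

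**Step 1: what the rule counts.** The safety panel, which includes potassium, is drawn at Visit 4 (baseline) and at Visits 6, 7 and 8, that is Weeks 4, 12 and 24 (study plan tables in both documents). A complete patient has three on-treatment values K1, K2, K3. With U the laboratory's upper limit:
- lowest value above U means K1 > U and K2 > U and K3 > U;
- highest value above U means at least one of them is above U.

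The two agree only when all values are high, when none is, or when there is a single value. An extra sample can only make the lowest-value condition harder to meet and the highest-value condition easier.

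**Step 2: a made-up patient.** Take potassium of 4.8 at baseline, 4.8 at Week 4, 5.9 at Week 12 and 4.7 at Week 24, with an upper limit anywhere from 5.0 to 5.5. The lowest value is 4.7, so the table records normal to normal. The value 5.9 is below 6.0, so it is not a marked abnormality either.

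**Step 3: do other displays count such a patient?**
- The marked-abnormality table and its listing start at 6.0 mmol/L.
- The change-from-baseline summary reports the centre and the single most extreme changes per arm. It does not count patients crossing the normal limit.
- Protocol 6.3.6 makes a laboratory deterioration an adverse event only if it is clinically significant, serious or the reason for stopping treatment.

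None of these counts moves from normal to between U and 6.0. Part of SAP 4.2.7.2.3 and some other laboratory text is blacked out, so this holds for the unredacted displays.

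**Step 4: size, on assumed inputs.** The upper limit and the potassium distribution are not in the documents. Assume mean 4.5 mmol/L, between-patient SD 0.3, within-patient SD 0.3, one baseline and three on-treatment values, no treatment effect and no missing samples. A shift to high requires baseline ≤ U and the chosen extreme > U. Simulated shares, with the expected number per 151 patients (the planned arm size) in brackets:

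| Assumed limit U | By highest value | By lowest value |
|---|---|---|
| 5.0 | 17.9% (0.179 × 151 = 27) | 0.8% (0.008 × 151 = 1.2) |
| 5.3 | 6.1% (0.061 × 151 = 9.2) | 0.1% (0.001 × 151 = 0.2) |
| 5.5 | 2.2% (0.022 × 151 = 3.3) | 0.02% (0.0002 × 151 = 0.03) |

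**Step 5: is this peculiar to those inputs?** A second set of assumptions fixes the chance p that any one value is above U at 3% to 15%, and the within-patient correlation at 0.3 to 0.7. Shifts to high are then 4.7% to 25.7% by highest value and 0.04% to 1.3% by lowest value. The planned rule would show about 1% to 8% of them. In the simple case of independent values and ignoring baseline, the shares are 1 − (1 − p)³ and p³. At p = 5% these are 1 − 0.95³ = 14.3% and 0.05³ = 0.01%.

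**The case against.** The sponsor could say the choice was deliberate. The lists differ by analyte, and the phosphate choice (highest only) matches a stated finding, since Protocol 1.3 reports more marked hyperphosphatemia with dapagliflozin. For potassium, the protocol describes a diuretic effect and possible electrolyte imbalance, and does not name hyperkalaemia among the risks. That is a fair reason to keep the lowest value. It is not a reason to leave out the highest, when sodium and calcium already have both.

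A reader might infer that the SAP contradicts itself, because 4.1.10 calls for the extreme in the direction of toxicity. The documents do not support that. Section 4.1.10 assigns no direction to potassium, exclusion 7 is an entry rule rather than an on-treatment definition of toxicity, and Appendix C limits both sides. Nor does the medication summary for "all concomitant ARB and/or ACE-I medication" in SAP 4.2.4 show that such treatment is common here; it only plans a table.

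The strongest objection concerns concealment of a treatment effect. Under the Step 4 assumptions the SD of change is 0.3 × √2 = 0.42. With 143 patients per arm (the sample-size figure), the standard error of the difference in mean change is 0.42 × √(2/143) = 0.05. A mean rise of 0.2 mmol/L in one arm would then be about 4 standard errors and plainly visible in the change-from-baseline summary. That objection stands: a general upward shift would not be hidden. What stays uncounted is the number of patients with rises that are not sustained, between the upper limit and 6.0.

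**Conclusion.** The point holds for this one table. As written, a shift to high potassium is counted only when every on-treatment value, or the only one, is above the limit, and the high column will understate such shifts. Under the assumptions tried, it would show roughly 1% to 8% of the shifts that the highest value would show. The direction follows from the definition and needs no assumption. The percentages depend on an assumed limit, distribution and complete sampling.

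Two stronger readings are tempting and should be resisted. One is that the table cannot show high potassium at all; sustained elevation, or a single high value in a patient with no other, does appear. The other is that the safety report would look reassuring whatever happened; a mean shift and values of 6.0 or more are reported elsewhere. No test, endpoint or named renal outcome (eGFR change, discontinuation for eGFR below 30) depends on this table, and SAP 3.4 plans no formal testing of safety variables. This is a free improvement to a descriptive display.

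**What to change.** In SAP 4.2.7.2.3, add potassium to the list of electrolytes tabulated by highest value and keep it in the list tabulated by lowest value. This gives two potassium shift tables, as already planned for sodium and calcium. The cost is one word in the SAP and one more output from samples already scheduled. Conduct, testing and patient management do not change.

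While the sentence is open, the sponsor should confirm that showing phosphate and magnesium by highest value only is intended, because the same logic means non-sustained shifts to low are not counted for them.
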